7.2 Judgment of the level of adverse events

All adverse events occurring during the trial will be judged for the severity according to CTCAEv5.0

Level 1: mild; no symptom or slight; only seen in clinic or diagnosis; no treatment is needed

Level 2: moderate; minor, local or non-invasive treatment is required; instrumental common daily activities appropriate to the age are limited*

Level 3: severe or important in medical meaning but not immediate life threatening; leading to stay or extension in hospital; causing disability; self-caring common daily activities are limited**

Level 4: life-threatening; emergent treatment is required

Level 5: AE-associated death

The semicolon (;) used in the description of the level means “or”.

Not all adverse events include all levels. Therefore, there are fewer than five levels for some adverse event to choose.

*instrumental common daily activities refer to cooking, shopping food or clothes, playing telephone, and making finance, etc.

**self-caring common daily activities refer to bathing, taking on/off clothes, eating, washing, taking medicine, etc. but without being bedridden.

7.3 Judgment for the causality with medicines

The relationship between adverse events and trial granules will be assessed according to the following 6-point classification criteria by the WHO-Uppsala Monitoring Centre (WHO-UMC) rating method: certain, likely, possible, unlikely, unclassified, unclassifiable.

Causal criteria for adverse events

Causality term	Assessment criteria
Certain	
 1. Event or laboratory test abnormality, with plausible time relationship to drug intake 2. Cannot be explained by disease or other drugs 3. Response to withdrawal plausible (pharmacologically, pathologically) 4. Event definitive pharmacologically or phenomenologically (i.e. an objective and specific medical disorder or a recognised pharmacological phenomenon) 5. Rechallenge satisfactory, if necessary
Likely	
 1. Event or laboratory test abnormality, with reasonable time relationship to drug intake 2. Unlikely to be attributed to disease or other drugs 3. Response to withdrawal clinically reasonable 4. Rechallenge not required
Possible	
 6. Event or laboratory test abnormality, with reasonable time relationship to drug intake 7. Could also be explained by disease or other drugs 8. Information on drug withdrawal may be lacking or unclear
Unlikely	
 9. Event or laboratory test abnormality, with a time to drug intake that makes a relationship improbable (but not impossible) 10. Disease or other drugs provide plausible explanations
Unclassified	
 11. Event or laboratory test abnormality 12. More data for proper assessment needed, or 13. Additional data under examination
Unclassifiable	
 14. Report suggesting an adverse reaction 15. Cannot be judged because information is insufficient or contradictory 16. Data cannot be supplemented or verified

7.4 Disposal of adverse events

(1) Observation and recording

Researchers should ask patients to truly report their condition changes after medication and avoid leading questions.

Any adverse reaction during the study should fill in the "adverse event form", and follow up investigation, record the treatment process and results in detail, until the laboratory examination returned to normal and the symptoms and signs disappeared. According to the severity of adverse reactions, the follow-up methods can be selected by hospitalization, outpatient service, home visit, telephone, communication and other forms.

(2) Medical management

When adverse reactions are found, the investigators should make decisions on diagnosis and treatment according to the patient's condition, and decide whether to discontinue the observation. In case of serious adverse events, the unit undertaking the clinical research must take necessary measures immediately to protect the safety of the subjects.

(3) Report

The investigators complete the serious adverse event report Form, and report it to the responsible institution and the ethics committee of their institution within 24 hours, and sign and date the report. The responsible unit of the project should timely inform the participating units and ensure that all the reporting procedures required by laws and regulations are met.

8. Quality control and warranty

8.1 Measures to prevent possible bias

Investigators should perform their duties and strictly follow the clinical research protocol and adopt standard operating procedures to ensure the implementation of the quality control and quality assurance system of the clinical research.

The sponsor shall employ 3 to 5 supervisors, who should have medical background, protect the rights and interests of the subjects participating in the clinical research, ensure the authenticity, accuracy and completeness of the research data recording and reporting, and ensure that the research complies with the designed research protocol and relevant regulations. The number of monitor visits should meet the needs of clinical research quality control. Monitors informed the project leader of the monitoring results after each visit.

The main measures for the possible bias in this study are as follows: to strengthen the training and monitoring of the researchers for the possible bias in the implementation of the study protocol in multi-center study; In view of the bias of researchers in the selection of subjects, a randomized design is adopted. In view of the bias of the researchers in the evaluation of the efficacy, the isolated evaluation is adopted, and the evaluation doctors are always blinded.

8.2 Measures to improve compliance of subjects

- (1) Researchers should carefully implement informed consent so that subjects can fully understand the requirements of the study and cooperate with the study. The physical and chemical examination fee is provided by the project fund.
- (2) Drug counting method is used to monitor the medication compliance of subjects. Compliance = (actual dosage/supposed dosage) ×100%. Adherence of less than 80% or more than 120% was considered to be a major protocol violation.
- (3) Patients will be reminded by telephone 2 days before the scheduled visit. The medicine is distributed by special personnel.

8.3 Investigator Training

Each research unit is responsible for organizing experts to train investigators on the study protocol before the start of the clinical study. Sign the investigator statement.

8.4 Quality control measures of test indicators

The laboratories of each participating hospital should establish standard operating procedures and quality control procedures for colonoscopy examination and laboratory observation indicators. The national legal units of measurement must be adopted for all laboratory tests in each participating hospital.

Laboratory test results must be printed on a computer with the date, test item, result, and normal range. Data should be traceable.

9. Data administration

9.1 Case Report Form (CRF)

In view of the fact that most outpatient medical records of hospitals in China are brought by patients, in order to preserve the primary data of clinical research completely, a special "Case Report Form" is designed for this study.

9.2 Data record

Requirements for CRF: ①Investigators must write CRF while treating subjects to ensure that the data are timely, complete, accurate and true. ②Any evidenced correction in the medical records of the study should only be underlined, and the revised data should be circumscribed and dated by the investigators, and the original records should not be erased or overwritten. ③ The laboratory results of both outpatients and inpatients should be filled in the "Physical and Chemical Examination Result Report Form" to the CRF. The original laboratory tests of subjects are pasted on the CRF.

Review of study medical records: After the end of the observation course for each subject, the researcher should submit the study medical record, informed consent and patient medication record card to the project leader of the unit within 3 working days for review, signature and storage, and timely deal with and record any problems found.

Data are reported using electronic CRF (Electronic Data Capture, EDC). The project leader of each center designates someone to undertake the work of "EDC entry clerk", which is responsible for the record of the first review of the research medical records and the registration and filling of the electronic CRF. The investigator must promptly hand over the study medical records to the "EDC entry clerk" after completing each subject observation. The "EDC entry clerk" must first review: whether the project record of the study medical record is complete and report on time.

9.3 Data monitoring

The monitoring frequency should meet the quality control requirements of clinical research. Monitors review each study record and complete "Monitor review pages" on a case-by-case basis.

Two monitors should 100% check the consistency of source data and electronic CRF data in the way of reading, and complete the "data consistency check report". If any errors are found in the data, the "Data Consistency Check Error Correction report" shall be submitted for correction by the electronic CRF data manager.

9.4 Data checking and blinding review

A database is established, including numerical ranges and logical checks. If there are any doubts, the query list will be filled out, and the questions in the query list will be answered by the researcher. Complete the data inspection report. The list of questions should be kept properly. After the blinded review report is completed, the database is locked. Documents related to quality control should be preserved, such as the original records of data consistency check, numerical range and logic check, the original records of blind review, and the records of questions communicated between researchers and monitors.

10. Statistical analysis

10.1 Statistical analysis plan and statistical software

Software SAS9.4 is used for statistical analysis.

The plan of statistical analysis will be made after the start of the study, and affirmed before the lock of the database. The plan will provide the content involved in all the statistical analysis, including the definition of dataset used for analysis, and statistical description and analytic methods used for different indicators, etc.

10.2 Selection of data sets for analysis

Full Analysis Set (FAS) refers to the ideal set of participants approaching as closely as possible to the analytic principle of intentionality (including all the cases randomized into the group, receiving at least one treatment of trial medicines, and having the evaluating data after administration). The missing data of the efficacy index in the visiting period will be supplemented with the method of Last Observation Carry Forward (LOCF).

Per Protocol Set (PPS) refers to the set of participants who meet the inclusion criteria in the trial treatment protocol, have good compliance, have not used the combined medicines that seriously affect the evaluation of efficacy, and not tremendously violated the trial protocol.

Safety Analysis Set (SS) refers to all cases that received at least one treatment with trial medicines after randomization, and had the data for safety evaluation post administration.

The division of statistical analytic dataset will be finalized in the conference of data review.

10.3 Content of Statistical analysis

The actual number of subjects in the two groups, dropout and exclusion cases, demographic and other baseline characteristics, compliance, efficacy analysis and safety analysis.

10.4 Statistical analysis methods

- (1) Descriptive statistical analysis: qualitative indicators are described by frequency table, percentage or constituent ratio. Quantitative indicators are described as mean, standard deviation, or median, lower quartile (Q1), upper quartile (Q3), minimum value, and maximum value.
- (2) Comparative analysis of the two groups: Chi-square test, Fisher's exact test, Wilcoxon rank sum test, CMH χ^2 test, WLS covariance are used for qualitative data. Quantitative data with normal distribution are tested by t test (homogeneity of variance test between groups, 0.05 is used as the test level, Satterthwaite method is used to correct the t test when the variance is not equal). Non-normal distribution is tested by Wilcoxon rank sum test, Wilcoxon signed rank sum test; GLM covariance. Two-sided test is used to test the hypothesis, and the test statistics and their corresponding P values are presented. $P \leq 0.05$ is considered statistically significant, and $P \leq 0.01$ is considered highly statistically significant.

11. Ethics

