11.6 The process of informed consent

The detailed information about the clinical trial should be explained, including the purpose of the trial, the trial procedure, the possible benefits and risks, and the rights and obligations of the subjects, etc., so that the subjects can fully understand and have sufficient time to consider, give consent after the questions have been answered satisfactorily, and sign the "informed consent" before starting the clinical trial. When each patient signs the informed consent form, the doctor will give his contact number to the patient, so that the patient can find the doctor at any time if his condition changes.

12. Summary and data preservation

Each research center is equipped with special file cabinets, and special personnel are responsible for keeping and sorting out the trial documents and related data. Special cabinets for trial drugs are set up, and special persons are responsible for drug registration, distribution and recovery. Investigators should submit the study medical records, informed consent forms, and patient medication record cards to the principal investigator of their centers within 3 days after the end of the observation course of each study case. Study data are uploaded to the data management center in accordance with relevant regulations. After the end of the study, all the research data are stored centrally in the project undertaking unit. The study is summarized by the blinded evaluators, and all the original data related to the study are saved by the research group and archived after the conclusion of the project.

13. Task allocation

Randomization is stratified by center, with block randomization. The study is conducted simultaneously in 8 hospitals including the Affiliated Hospital of Nanjing University of Traditional Chinese Medicine (team leader), Beijing Friendship Hospital Affiliated to Capital Medical University, Longhua Hospital Affiliated to Shanghai University of Traditional Chinese Medicine, Guangdong Provincial Hospital of Traditional Chinese Medicine, the First Affiliated Hospital of Nanjing Medical University, Shuguang

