Hospital Affiliated to Shanghai University of Traditional Chinese Medicine, Changhai Hospital Affiliated to Naval Medical University, and the First Affiliated Hospital of Guangzhou University of Traditional Chinese Medicine. The random arrangement of 400 subjects to receive treatment is generated by an independent third-party with the help of SAS statistical analysis system. The basic information of the cases is input by each member unit, and the eligible cases are automatically assigned to the treatment group or the control group and received corresponding treatment.

Hospital	Planned number of cases assigned
Affiliated Hospital of Nanjing University of Chinese Medicine	112
Guangdong Provincial Hospital of Traditional Chinese Medicine	84
Longhua Hospital Affiliated to Shanghai University of Traditional Chinese Medicine	52
Shuguang Hospital Affiliated to Shanghai University of Traditional Chinese Medicine	76
the First Affiliated Hospital of Guangzhou University of Traditional Chinese Medicine	48
Affiliated Hospital of Naval Military Medical University	16
Beijing Friendship Hospital, Capital Medical University	8
the First Affiliated Hospital of Nanjing Medical University	4
Total	400

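### Randomisation is stratified by centre, but section 10.4 does not commit the primary endpoint to a centre-stratified test or to a between-group estimate with a confidence interval

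*Combined protocol and SAP*

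**What the plan says.** Section 13 (Task allocation) states: "Randomization is stratified by center, with block randomization". Section 3.4 also describes stratified block randomisation, 1:1 within blocks, without naming the factor. The table in section 13 headed "Planned number of cases assigned" gives the eight hospitals 112, 84, 52, 76, 48, 16, 8 and 4 patients, 400 in all.

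The primary endpoint (section 6.2) is binary: whether a patient has a new adenoma at colonoscopy over two years. Section 10.4 assigns methods by data type, not by endpoint. For qualitative data the list runs "Chi-square test, Fisher's exact test, Wilcoxon rank sum test, CMH" and ends with a WLS covariance method. No item is linked to the adenoma detection rate, CMH has no stratifying variable and WLS has no covariate. Within groups, "qualitative indicators are described by frequency table, percentage or constituent ratio". Between groups, "the test statistics and their corresponding P values are presented". No section supplied mentions a risk difference, risk ratio, odds ratio, confidence interval or adjustment for centre.

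Section 10.1 defers detail: "The plan of statistical analysis will be made after the start of the study, and affirmed before the lock of the database". That plan is to cover "statistical description and analytic methods used for different indicators". Section 9.4 adds: "After the blinded review report is completed, the database is locked". The later plan is not among the documents supplied.

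**The concern.** Stratified randomisation balances the arms within each centre, so differences in detection rate between centres contribute almost nothing to the treatment comparison. An unstratified chi-square test still counts that between-centre variation in its standard error. The standard error is then too large, the test rejects too rarely under the null, and the interval is wider than it need be. The design has already provided the precision; the analysis has to use the stratification to recover it.

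Two further things are at stake. Three tests that could serve for the primary comparison (chi-square, Fisher, CMH) remain open, and they do not always agree at 0.05. Also, the protocol's stated purpose is evidence for clinical guidelines, and guideline users need the size of the effect and its uncertainty, which a P value does not give. A reader can work out an unadjusted interval from group counts. A centre-adjusted one needs counts by centre, which section 10.4 does not mention.

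**Working it through.** **Inputs.** From section 3.3: control rate 52%, reduction 34%, alpha 5%, power 90%, dropout 20%, 160 per group, 400 randomised. From section 10.4: two-sided testing. From section 13: the eight centre sizes. Assumed: the SD of centre effects on the log-odds scale, which the documents do not give.

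**1. The plan's own figure.** Reading 34% as a relative reduction, the treated rate is 0.52 × 0.66 = 0.3432 and the difference is 0.1768. With (1.960 + 1.282)² ≈ 10.507 and unpooled variance:

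n = 10.507 × (0.52 × 0.48 + 0.3432 × 0.6568) / 0.1768² = 10.507 × 0.4750 / 0.03126 = 159.7, so 160 per group.

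Pooled variance gives 162.8. Dropout: 160 / 0.8 = 200 per group, 400 in total. The stated size reproduces as an unstratified two-proportion comparison.

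**2. The estimate at the design rates.** With 160 per group, SE = √(0.4750/160) = 0.0545. The risk difference is −17.7 points (95% CI −28.4 to −7.0), and the risk ratio is 0.66 (0.51 to 0.86).

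**3. Tests compared by simulation.** Patients were allocated 1:1 within the planned centre sizes, each evaluable with probability 0.80, with normal centre effects on the logit scale. The intercept was solved in each trial so that the size-weighted overall rates stayed at 52% and 34.3% (52% in both arms for type I error). There were 400,000 trials per scenario.

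- Unstratified: Pearson chi-square without continuity correction; Wald interval for the risk difference.
- Stratified: with a_k events among n1k treated patients, n0k controls, and m_k events among all T_k patients in centre k, Z = Σ(a_k − n1k·m_k/T_k) / √Σ[n1k·n0k·m_k(T_k − m_k) / (T_k²(T_k − 1))]. The Mantel-Haenszel risk difference uses weights n1k·n0k/T_k and the Sato variance. There were six strata: five large centres, and the centres of 16, 8 and 4 pooled.

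| Assumed centre SD | Power %, chi-square / CMH | Type I error %, chi-square / CMH | Mean 95% CI width in points, unadjusted / Mantel-Haenszel |
|---|---|---|---|
| 0 | 89.4 / 89.3 | 5.1 / 5.0 | 21.3 / 21.3 |
| 0.25 | 89.6 / 89.6 | 4.9 / 5.0 | 21.3 / 21.2 |
| 0.5 | 89.9 / 90.5 | 4.7 / 5.0 | 21.3 / 20.9 |
| 0.75 | 90.3 / 91.8 | 4.2 / 4.9 | 21.3 / 20.4 |
| 1.0 | 90.7 / 93.0 | 3.7 / 4.9 | 21.3 / 19.9 |

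The unadjusted interval covers 94.8%, 95.3% and 96.1% of the time at SD 0, 0.5 and 1.0; the Mantel-Haenszel interval stays at 94.8 to 94.9%. Leaving all eight centres unpooled changes power by less than 0.1 point.

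On scale: the log-odds of 0.52 is 0.08, so an SD of 1.0 puts control rates at roughly 28% and 75% for centres one SD either side.

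**4. How often the choice changes the verdict.** Under the planned effect, chi-square and CMH disagree at 0.05 in 0.8% of trials at SD 0 and 2.9% at SD 1.0. By exact enumeration at 160 per group, chi-square and Fisher disagree in 2.2% (1.2% under no effect). Fisher has power of 87.0% against 89.2%, and type I error of 3.8% against 5.0%.

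**5. Sensitivity to calibration.** Fixing the rates for an average centre instead of overall (40,000 trials, eight strata) gives power, chi-square / CMH, of 86.5 / 87.6% at SD 0.5, 82.3 / 85.2% at SD 0.8 and 73.4 / 80.5% at SD 1.2. This calibration also shrinks the overall effect as the SD grows, so the smaller gains in the table are used here.

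**The case against.** The strongest reply is that the protocol assigns this decision to a plan finalised before lock. That plan is not in hand and may already name a centre-stratified CMH test and an interval. This stands: the point is about what the protocol text commits to, and nothing shows that the choice would be made on unblinded data.

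Next, CMH for a two-arm binary outcome has little purpose without strata, and centre is the only stratifying factor named, so the list arguably implies the right analysis. Fisher is normally kept for sparse tables, which these would not be. Both remarks are fair, and the Fisher figures describe an unlikely choice. An implied use is still not a stated primary test.

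Finally, the gain is small. Chi-square power stays between 89.4% and 90.7% against a 90% target, type I error is not materially inflated, and the larger gains need a spread between centres that nothing in the documents supports. All of that is correct. It limits the priority of the point. It does not argue for leaving the design factor out of the analysis when including it costs almost nothing.

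**Conclusion.** The point holds. The protocol stratifies by centre but does not commit the primary endpoint to an analysis that uses centre, and it commits to no between-group estimate or interval. This does not threaten validity or the sample size: the unstratified test is sound, and conservative if centres differ. What is given up is precision. The power loss is none to about 2.3 points over an assumed centre SD of 0 to 1.0, and under 1 point up to 0.5. The interval is up to 1.4 points wider than needed (21.3 against 19.9). That SD range is an assumption and not a bound, and the figures also rest on the planned centre sizes, 80% evaluable patients and a 34% relative reduction. It is a worthwhile improvement at almost no cost.

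**What to change.** In section 10.4, or in the analysis plan that section 10.1 requires before lock:

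- Name the two-sided Cochran-Mantel-Haenszel test stratified by centre as the single primary test of the adenoma detection rate.
- Fix, before unblinding, a rule for pooling very small centres and apply it to actual recruitment. One example is fewer than 20 randomised patients, which on planned numbers pools the centres of 16, 8 and 4. The exact threshold matters little.
- Report the Mantel-Haenszel risk difference and risk ratio with 95% confidence intervals.
- Use the other listed tests for this endpoint only as sensitivity analyses.

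A model with centre as a covariate would be equally sound; CMH is suggested because it is already listed. No new data are needed, since centre is known for every patient. In the pre-lock plan the change is wording only. If section 10.4 itself is amended, section 11.1 requires resubmission to the ethics committee. If centres turn out not to differ, the cost is about 0.1 point of power (89.4% against 89.3%).

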Administration Plan	
Treatment group: Shenbai Granules, 1 pack/time, 2 times a day, for 6 months
 
Control group: placebos, 1 pack/time, 2 times a day, for 6 months

Effectiveness Indicators	
Primary indicator: The adenoma detection rate during follow-up for 2 years
 
Secondary indicator:
 
 (1) The detection rate of any polypoid lesions during follow-up for 2 years (2) The detection rate of high-risk adenomas during follow-up for 2 years

	(3) The detection rate of sessile serrated lesions during follow-up for 2 years
Safety indicators	
 1. Physical examination 2. Laboratory test (blood and urine routine, liver and kidney function) 3. Adverse events
Statistical Analysis	General information will be analyzed with ITT data, effectiveness with mITT and PPS data respectively, and safety with SS data.

Study visits flow chart

Study phase Project	Screening period	Treatment period			
	Baseline (-1m to 0)	Visit 1 (3m ± 1w)	Visit 2 ^a (12m ± 2w)	Visit 3 (15m ± 2w)	Visit 4 ^b (24m ± 2w)
Obtaining informed consent form	•				
Demographics	•				
Determination of inclusion and exclusion criteria	•				
Filling in general information	•				
Concomitant disease and medication before treatment	•				
Physical examinations	•	•	•	•	•
Colonoscopy and polypectomy ^c	•		•		•
Histological diagnosis	•		•		•
Boston score	•		•		•
withdrawal time	•		•		•
Blood routine	•	•	•	•	
Urine routine	•	•	•	•	
Liver function	•	•	•	•	
Renal function	•	•	•	•	
Urine pregnancy test (women)	•		•		
Distribution of trial granules	•		•		
Recovery of trial granules		•		•	
Adverse events		•	•	•	•

Concurrent medication records	•	•	•	•	•
Reason for dropouts		•	•	•	•

^a The first subsequent colonoscopy should be performed around 1 year after baseline colonoscopy.

^b The second subsequent colonoscopy should be performed around 2 years after baseline colonoscopy.

^c Each colonoscopy should have adequate bowel preparation, reach the ileocecal region and have a withdrawal time of more than 6 minutes. All polyps detected should be removed and evaluated completely.

1. Background

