3.3 Sample size

According to the literature search and previous research results, the average detection rate of recurrent adenomas without agent intervention for patients after polypectomy is 52%. We hope that ADR will be reduced by 34% after intervention of SBG. With a significance level (alpha) of 5% and power of 90%, the patient number needed is 160 in each group. Allowing for 20% of participants to drop out, the target number of participants to be randomly assigned is 400.

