6.1 General observation

- (1) Demographic characteristics: sex, age, job, address, phone, etc.
- (2) Vital signs: temperature, resting heart rate, respiration, blood pressure (systolic pressure, diastolic blood pressure).
- (3) Chronic disease related information.

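### Section 10.4 commits the primary adenoma detection rate to no covariate-adjusted analysis and names no covariates or strata, so collected baseline data that could add precision may go unused

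*Combined protocol and SAP*

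**What the plan says.** Section 6.2 defines the primary endpoint as a proportion: patients with a new adenoma over two years, out of all patients in the group. Section 10.4 then lists methods by type of data, not by endpoint. For categorical data it names the chi-square, Fisher and rank-sum tests and CMH, and ends with "WLS covariance are used for qualitative data". It adds "Two-sided test is used to test the hypothesis". No method, stratum, covariate or effect measure is tied to the adenoma detection rate.

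Section 10.1 leaves the detailed analysis plan to be written after the trial starts and confirmed before database lock.

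Baseline information is collected. Section 6.1 has "Demographic characteristics: sex, age, job" among its items. The visit flow chart marks colonoscopy and histology at baseline, and its footnote c adds "All polyps detected should be removed and evaluated completely". Section 4.1 classes adenomas as tubular, tubulovillous or villous. Section 13 stratifies randomisation by centre, and section 10 does not mention centre.

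**The concern.** A covariate that predicts recurrence explains part of the outcome variance, and an analysis that uses it estimates the same difference in rates more precisely. Randomisation is stratified by centre only, so the design does not balance baseline adenoma risk. If the final analysis is a plain chi-square, it leaves unused information that the trial has already collected, and it ignores the stratification.

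There is also a timing problem. Covariates are credible only if they are named before the data are unblinded. If the arms turn out to differ visibly at baseline, adjustment chosen afterwards will carry little weight, and an open list lets adjusted and unadjusted results compete for the headline.

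**Working it through.** **1. The plan's own sample size.** Inputs from section 3.3: a control rate of 52%; an effect worded as "We hope that ADR will be reduced by 34% after intervention of SBG"; alpha 0.05; 90% power; 160 per arm; 20% dropout; 400 randomised. Section 10.4 makes the test two-sided.

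Reading the 34% as relative, the treated rate is 0.52 × 0.66 = 0.3432 and the difference is 0.1768. The sum of the two binomial variances is 0.52 × 0.48 + 0.3432 × 0.6568 = 0.4750. With unpooled variance, n = 0.4750 × (1.960 + 1.282)² / 0.1768², which rounds up to 160 per arm. Then 160 / 0.80 = 200 per arm, 400 in total. The stated figures reproduce, from a two-proportion comparison with no covariates. An absolute fall of 34 points (to 18%) would need only about 40 per arm, so the relative reading is the one that fits.

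**2. Unadjusted power at 160 per arm.** The standard error of the difference is √(0.4750 / 160) = 0.0545, or 5.45 points. With the pooled-variance test, power is 89.5%, and 163 per arm are needed for 90%. If all 200 per arm contribute, power is 94.9% and there is less to gain.

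**3. Adjustment, by formula.** The documents do not say how well any baseline variable predicts recurrence, so R² is an assumption. Both standard errors are multiplied by √(1 − R²), and the required n is 163 × (1 − R²).

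| Assumed R² | Power at 160 per arm | n per arm for 90% |
|---|---|---|
| 0 | 89.5% | 163 |
| 0.02 | 90.1% | 160 |
| 0.05 | 90.9% | 155 |
| 0.10 | 92.3% | 147 |
| 0.15 | 93.7% | 139 |
| 0.20 | 94.9% | 131 |

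**4. Adjustment, by simulation.** 160 per arm, one normally distributed covariate, 4,000 trials per row, Monte Carlo error about 0.5 point. Adjusted power is for the arm coefficient in the logistic model; the variance is that of the standardised risk difference.

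| Assumed odds ratio per SD | Unadjusted power | Adjusted power | Fall in variance |
|---|---|---|---|
| 1.3 | 88.4% | 89.2% | 2% |
| 1.6 | 88.5% | 90.3% | 4% |
| 2.0 | 89.4% | 92.6% | 9% |
| 2.5 | 89.7% | 93.7% | 16% |

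With a covariate of no prognostic value the variance ratio was 1.001, so nothing was lost.

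A second simulation (3,000 trials per setting) assumed that 40% of patients have a higher-risk baseline finding (odds ratio 1.5 to 3) and an age odds ratio of 1.2 to 1.5 per SD. Variance fell by 2% to 9%. Adjusted power was 90.2% to 92.1%, against 88.6% to 89.9% unadjusted. The variance reduction equals about 160 × (1/0.98 − 1) = 3 to 160 × (1/0.91 − 1) = 16 extra patients per arm.

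**5. Chance imbalance.** Assume a risk factor with 40% prevalence. The SD of its between-arm difference is √(2 × 0.4 × 0.6 / 160) = 0.0548, so the 95% range is ±10.7 points. If the factor changes recurrence by 20 to 22 points, a 1.96-SD imbalance moves the raw difference by 2.1 to 2.4 points. The 95% half-width of the raw difference is 1.96 × 5.45 = 10.7 points. At 2.4 points this source is (2.4 / 10.7)² = 5% of the variance, and it is already inside the standard error.

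**6. Not quantified.** Neither simulation includes centre, because the documents give no between-centre variation in recurrence.

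**The case against.** A reader might infer that the primary comparison will be unadjusted. The documents do not say so. CMH is a stratified method, and the covariance method quoted above is an adjustment method; both stand in the same list as the chi-square. The covariate-free sample-size calculation hints at a simple test but commits to nothing. Section 10.1 also promises methods for each indicator in a later plan, which may name covariates.

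A reader might also infer that chance imbalance would bias an unadjusted result. It would not. Under randomisation the unadjusted test keeps its type I error, and the imbalance contributes only the small share of variance shown in step 5. The planned size already gives about 89% to 90% power without adjustment.

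All of this stands, and it limits the point to precision and pre-specification. It does not remove it: nothing in the documents names the primary method, its strata or its covariates, so the text permits the least efficient option, and equally a set of covariates chosen late.

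**Conclusion.** The plan leaves open whether the primary adenoma detection rate is adjusted at all, and for what. Under the assumed prognostic strengths, committing to adjustment lowers the variance by about 2% to 9%, up to 16% for a stronger predictor, and adds about 1 to 4 power points at 160 per arm from a base of about 89%. This is a modest gain at almost no cost, so the change should be made, but the trial's validity does not depend on it.

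Two further inferences go beyond the documents. One is that the recorded variables are strong predictors of recurrence: no section gives their prognostic strength, so they are best called potentially prognostic. The other is that WLS cannot carry covariates: that depends on the form meant. A WLS analysis of cross-classified tables needs filled cells, whereas a randomisation-based form can take a continuous covariate. Section 10.4 does not say which is intended, and that is all that can be held against it.

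**What to change.** In section 10.4 and the analysis plan, before database lock and unblinding:

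- Name one primary analysis: a logistic model for any new adenoma with arm, centre, age, sex and baseline histology. Code histology as tubulovillous or villous under section 4.1 versus tubular, with a rule for patients with several lesions.
- State how small centres are pooled. Section 13 plans 4, 8 and 16 cases at three sites. Joined, they make one stratum of 28 beside the sites with 112, 84, 76, 52 and 48.
- Add the number of baseline adenomas only if the CRF records it; the protocol does not list it as a variable.
- Report the standardised (marginal) risk difference with its 95% confidence interval, so that the result still estimates the difference in section 6.2 rates.
- Keep the unadjusted comparison as supportive.
- Define WLS covariance wherever it is retained.

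The model is affordable. At the planned rates, 160 × (0.52 + 0.3432) = 138 events are expected. With six centre strata there are 5 + 4 = 9 coefficients besides the intercept, about 15 events for each. The cost is wording and a few lines of SAS, with no new data collection.
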